12.1 Quality Control

Quality control should be applied to each stage of data handling to ensure that all data are reliable and have been processed correctly. The investigational site is responsible for performing regular Quality Control checks on the data they generate. Additionally, the sponsor will perform risk based monitoring of this study, and associated Quality Control checks, as described in the Monitoring Plan.

QC will be applied to each stage of data handling to ensure that all data are reliable and have been processed correctly:

- Laboratory staff will be trained in data collection and entry
- All source documentation will be filed and preserved
- All assay results will be recorded onto paper laboratory CRFs immediately following testing
- All data will be double entered from the paper CRF to the eCRF by two on-site staff
- Electronic data will be backed up daily
- The Co-investigator will review all data entered for the site's samples

- The Trial Manager and Data Manager will perform periodic data checks to ensure all paper and electronic records are complete and input data are consistent and accurate

12.2 Quality assurance

As part of routine QA, the sponsor (FIND) or designee may conduct an audit of the investigational site. Monitoring visits may include, but are not limited to, review of regulatory files, laboratory reports, and protocol compliance. Study monitors will meet with co-investigators to discuss any problems and actions to be taken and document visit findings and discussions.

FIND will provide training on data collection and entry, implement quality control procedures related to the data entry system and generate data quality control checks that will be run on the database. Any missing data or data anomalies will be communicated to the laboratory for clarification and resolution. The laboratory will provide direct access to all source data/documents for the purpose of monitoring and auditing by the sponsor by local and regulatory authorities, if requested.

12.3 Study and Site Closure

The sponsor designee reserves the right to close the study site or terminate the study at any time for any reason at the sole discretion of the sponsor. Study sites will be closed upon study completion. A study site is considered closed when all required documents and study supplies have been collected and a study-site closure visit has been performed.

The investigator may initiate study-site closure at any time, provided there is reasonable cause and sufficient notice is given in advance of the intended termination.

Reasons for the early closure of a study site by the sponsor or investigator may include but are not limited to:

- Failure of the investigator to comply with the protocol, the requirements of the IRB/IEC or local health authorities, the sponsor's procedures, or GCP guidelines
- Inadequate recruitment of participants by the investigator
- Discontinuation of further study intervention development

13 Publication Policy

Authorship will be determined by mutual agreement and in line with International Committee of Medical Journal Editors authorship requirements, as described in the

publication policy section of the contractual agreement. Briefly, results of this study will be submitted for publication in peer reviewed journals as soon as feasible upon completion of the study. Appropriate attributions (i.e. co-authorship or acknowledgement regarding the generation of data as the case may be) will be made in all publications related to this study. Authorship determination will be in accordance with the guidelines provided by the International Committee of Medical Journal Editors.

Before a paper or abstract is submitted for publication, the other party shall be provided thirty (30) days to review the proposed publication or disclosure to assure that Proprietary/Confidential Information is protected and to prevent, at its sole discretion, any publication of the party's own Proprietary/Confidential Information. In the event that Cepheid desires to protect any of the information disclosed in the proposed publication, then FIND agrees to delay publication by an additional 60 days or such other reasonable amount of time as required to allow Cepheid to make any applicable filings.

14 References

- 1 World Health Organization. Global tuberculosis report 2015. 2015
DOI:10.12987/yale/9780300190298.001.0001.
- 2 World Health Organization. Report: Multidrug-resistant tuberculosis (MDR TB).

Appendix 1: Safety Definitions and Reporting

Appendix 2: Incident Definition and Reporting

Appendix 3: Protocol Amendment Summary Table

Appendix 4: Sample Requirement to Achieve Target Sample Size

Appendix 5: Definitions of Diagnostic Test Results

Appendix 1: Safety Definitions and Reporting

Adverse Event (AE) Definition

 An AE is any unfavorable and unintended sign (including abnormal laboratory finding), symptom or disease temporally associated with the use of an investigational product, whether or not related to the investigational product.

Serious Adverse Event (SAE) Definition:

a. Results in death

b. Is life-threatening
 
The term 'life-threatening' in the definition of 'serious' refers to an event in which the participant was at risk of death at the time of the event. It does not refer to an event, which hypothetically might have caused death, if it were more severe.

c. Requires inpatient hospitalization or prolongation of existing hospitalization
 
In general, hospitalization signifies that the participant has been detained (usually involving at least an overnight stay) at the hospital or emergency ward for observation and/or treatment that would not have been appropriate in the physician's office or outpatient setting. Complications that occur during hospitalization are AEs. If a complication prolongs hospitalization or fulfils any other serious criteria, the event is serious. When in doubt as to whether "hospitalization" occurred or was necessary, the AE should be considered serious.
 
Hospitalization for elective treatment of a pre-existing condition that did not worsen from baseline is not considered an AE.

d. Results in persistent disability/incapacity
 
 The term disability means a substantial disruption of a person's ability to conduct normal life functions. This definition is not intended to include experiences of relatively minor medical significance such as uncomplicated headache, nausea, vomiting, diarrhea, influenza, and accidental trauma (e.g., sprained ankle) which may interfere with or prevent everyday life functions but do not constitute a substantial disruption.

e. Is a congenital anomaly/birth defect


f. Other situations:
 
 Medical or scientific judgment should be exercised in deciding whether SAE reporting is appropriate in other situations such as important medical events that may not be immediately life-threatening or result in death or hospitalization but may jeopardize the participant or may require medical or surgical intervention to prevent one of the other outcomes listed in the above definition. These events should usually be considered serious. 
Examples of such events include intensive treatment in an emergency room or at home for allergic bronchospasm or convulsions that do not result in hospitalization, or development of drug dependency or drug abuse.

SAE Reporting to FIND

- The SAE Report must be sent to the FIND Head of Program and Trial Manager via e-mail, marked High Priority, with a follow up call to ensure receipt.
- Initial notification via telephone does not replace the need for the investigator to complete and sign the SAE Report within the designated reporting time frames.
- Contacts for SAE reporting can be found on the front of the protocol.

Appendix 2: Incident Definition and Reporting

Medical Device/IVD Incident Definition

- A medical device incident is any malfunction or deterioration in the characteristics and/or performance of a device or IVD as well as any inadequacy in the labeling or the instructions for use which, directly or indirectly, might lead to or might have led to the death of a participant/user/other person or to a serious deterioration in his/her state of health.
- Not all incidents lead to death or serious deterioration in health. The nonoccurrence of such a result might have been due to other fortunate circumstances or to the intervention of health care personnel.

It is sufficient that:

- An **incident** associated with a device happened.

AND

- The **incident** was such that, if it occurred again, might lead to death or a serious deterioration in health.

A serious deterioration in state of health can include any of the following:

- Life-threatening illness
- Permanent impairment of body function or permanent damage to body structure
- Condition necessitating medical or surgical intervention to prevent one of the above
- Fetal distress, fetal death, or any congenital abnormality or birth defects

Medical Device Incident Documenting

- Any medical device incident occurring during the study will be documented in the participant's medical records, in accordance with the investigator's normal clinical practice, and on the appropriate form of the CRF.
- For medical device incidents fulfilling the definition above, complete the SAE Report Form.
- It is very important that the investigator provides his/her assessment of causality (relationship to the medical device provided by the sponsor) and describes any corrective or remedial actions taken to prevent recurrence of the incident.
- A remedial action is any action other than routine maintenance or servicing of a medical device where such action is necessary to prevent recurrence of an incident. This includes any amendment to the device design to prevent recurrence.

Appendix 3: Protocol Amendment Summary Table

The Protocol Amendment Summary of Changes Table for the current amendment is located directly before the Table of Contents (TOC).

Amendment [amendment number]: ([date])

Overall Rationale for the Amendment

[Rationale]

Section # and Name	Description of Change	Brief Rationale

Appendix 4: Sample Requirement to Achieve Target Sample Size

	MTB+ group*		Additional RIF-R group		TOTAL
Samples Tested	100%	360	100%	400	760
Invalid Xpert Ultra results	1%	4	1%	4	8
Culture-contaminated	10%	36	10%	40	76
Molecular-test non-determinant*	10%	36	10%	40	76
Included**	79%	284	79%	316	600
INH-resistant	29%	82	99%	313	395
INH-sensitive	71%	202	1%	3	205
FQ-resistant	5%	14	25%	79	93
FQ-sensitive	95%	270	75%	237	507
AMK/CAP-resistant	2%	6	9%	28	34
AMK/CAP-sensitive	98%	278	91%	288	566
KAN-resistant	1%	3	21.5%	68	71
KAN-sensitive	99%	281	78.5%	248	529

*Assume 23% of TB-positive samples are RIF-R based upon previous studies and data from these regions^{11,13}.

**We assume 29% INH resistance, 5% FQ resistance and 1-2% second-line injectable (AMK, KAN and CAP) resistance among TB-positive patients based upon previous studies and data from these regions^{11,13}. Testing 284 TB-positive specimens (based on Xpert MTB/RIF and Ultra-testing) would then be expected to yield 82 INH-resistant but only 14 FQ-resistant specimens and 3-6 second-line injectable-resistant specimens (limiting factor in sample size calculations). This allows for determination of Xpert MTB/XDR performance for INH resistance detection as a reflex test to any TB-positive result, but is not sufficient for determination of Xpert MTB/XDR performance for second-line resistance detection. To efficiently get to a sufficient number of second-line resistant samples, we will supplement this by testing 316 additional RIF-resistant samples. To account for contaminated cultures and invalid/non-determinant Xpert MTB/RIF or Ultra, NGS and Xpert MTB/XDR results, we would inflate these numbers by 21%, leading to a total of 360 TB-positive and 400 additional RIF-resistant samples, i.e. a total of 760 patient samples tested in this study.

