Rapid diagnostics for second-line drug resistance detection identify mutations in the *gyrA* and *gyrB* genes⁷, associated with fluoroquinolone resistance, and *rrs* and *eis* gene regions, associated with second-line injectable resistance (with *eis* promoter mutations exclusively associated with KAN resistance)⁸. Recently, a novel GeneXpert cartridge was developed to detect mutations occurring in these genes, as well as in the *katG* and *inhA* gene regions, associated with INH resistance⁹. A Research Use Only (RUO) version of the Xpert MTB/XDR cartridge showed promising performance for INH and second-line resistance detection in a clinical evaluation study (sensitivity 92.7-98.1%; specificity 94.3-99.6%)¹⁰. The assay chemistry has since been improved and additional gene targets have been added to the assay to improve the detection of INH resistance (i.e. *fabG1* and *ahpC*).

Evidence of assay accuracy from an external laboratory validation using a well-characterized set of Mtb strains as well as from large-scale, multicentre clinical studies is needed to confirm the validity of the most recent Xpert MTB/XDR assay for INH and second-line resistance detection, and to recommend its use in diverse clinical settings. The focus of this protocol is the multicentre clinical evaluation.

2 Study Objectives and Endpoints

Objectives	Data Collected	Endpoint
Primary		
1.1 Estimate the diagnostic accuracy of the Xpert MTB/XDR assay for INH and ETH resistance detection , for a clinically diverse set of TB samples, with phenotypic DST and katG , fabG1 , ahpC and inhA	284 Xpert MTB/RIF TB-positive and 316 RIF-resistant clinical samples tested by Xpert MTB/XDR, phenotypic DST and NGS	1.1 Sensitivity and specificity estimates for INH and ETH resistance detection

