3.4 End of Study Definition

Phase II will be considered completed once all *in vitro* diagnostic (IVD) testing has completed and all culture, DST and NGS results have been returned for at least 284 TB-positive and 316 additional RIF-resistant clinical samples, and all user appraisal questionnaires have been completed at the three clinical sites.

4 Study Population and Eligibility

Individuals who have one or more risk factors for DR-TB presenting to participating centres will be screened by Xpert MTB/RIF or Ultra. Those who test MTB-positive by Xpert MTB/RIF or Ultra at the study sites will be asked to participate. Once at least 360 MTB-positive patients have been tested, an additional subset of Xpert MTB-positive, RIF-resistant patients (n=400) will also be asked to participate in this study. Individuals will be recruited at outpatient clinic settings and inpatient hospital settings. Individuals will be asked by non-study clinicians or staff if they would be interested in participating in the study. Interested individuals will be referred to study personnel for additional information and screening, if appropriate. HIV-positive individuals and HIV-negative individuals will be included in this study.

Prospective approval of protocol deviations to recruitment and enrolment criteria, also known as protocol waivers or exemptions, is not permitted.

4.1 Inclusion Criteria:

Patients meeting the following criteria will be screened by Xpert MTB/RIF or Xpert MTB/RIF Ultra:

- Age 18 years or above;
- Symptoms suggesting pulmonary TB, i.e. persistent cough (generally ≥ 3 weeks or as per local definition of TB suspect), **and** at least one of the following:
 - Previously received >1 month of treatment for a prior TB episode **or**
 - Failing TB treatment with positive sputum smear or culture after ≥ 3 months of a standard TB treatment **or**
 - Had close contact with a known drug-resistant TB case **or**
 - Newly diagnosed with MDR-TB within the last 30 days **or**
 - Previously diagnosed with MDR-TB and failed TB treatment with positive sputum smear or culture after ≥ 3 months of a standard MDR-TB treatment regimen

Patients meeting the above criteria will be screened by Xpert MTB/RIF or Xpert MTB/RIF Ultra. TB patients meeting the following criteria will be included in the study:

- A clear Mtb-positive and RIF-resistant or RIF-sensitive result by Xpert MTB/RIF or Xpert MTB/RIF Ultra
- Provision of informed consent;

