5.3 Minimization of Error and Bias

5.3.1 Patient Selection

A consecutive series of Xpert MTB/RIF MTB-positive patients (n=284) will be enrolled in this study, followed by an additional, consecutive series of Xpert MTB/RIF RIF-resistant patients (n=316) between the three countries with participating clinical sites. Enrolment will be based upon clearly defined eligibility criteria.

Analyses will be conducted for relevant sub-groups of the enrolled TB patient population (i.e. smear status for TB, drug-resistance profile, mutations detected, etc.), which may be considered to be indicators of disease severity.

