6.1.2 Study Workflow

Study flow is shown in Figure 1. All available Xpert MTB/RIF TB-positive samples will be tested in this study (i.e. consecutive patient samples) until sample size targets are met. All molecular assays will be performed in accordance with SOPs provided by the manufacturers. Specimen handling and processing by routine tests will be carried out according to NTP local policies and standards.

Samples will first be tested by Xpert MTB/RIF or Ultra, as part of routine diagnostic procedures. This Xpert MTB/RIF step will act as a screening tool for trial enrolment. Participants testing positive for MTB by Xpert MTB/RIF will be asked to volunteer for the Xpert MTB/XDR trial. This (testing of specimens from TB-positive samples) is in line with the intended use of the XDR assay as an add-on test to the Xpert MTB/RIF assay.

[figure not shown]
A staged enrolment will proceed: Stage 1 will enrol 360 MTB-positive participants, irrespective of RIF resistance/sensitivity. Once enrolment is complete, Stage 2 will enrol 400 MTB-positive RIF-resistant participants (see section 9.1 and Appendix 4: Sample Requirement to Achieve Target Sample Size). This staging is designed to better evaluate Xpert MTB/XDR sensitivity for second-line resistance detection.

In order to efficiently assess the diagnostic performance of the Xpert MTB/XDR assay, participants will be asked to provide ≥ 3 ml of sputum (either a single sputum or two consecutively collected and pooled sputa). Samples will be homogenized and split for testing.

The Xpert MTB/XDR assay and acid-fast bacilli smear will be performed on the direct sample. 2ml of sputum will be decontaminated and used for MGIT and LJ culture.

Following direct testing, phenotypic MGIT DST will be performed for all culture-positive samples for INH, RIF, fluoroquinolone (moxifloxacin and levofloxacin), AMK, ETH (ethionamide), KAN and CAP. Cultured samples will also undergo subsequent molecular testing by LPA and targeted NGS of relevant gene regions (*katG*, *inhA*, *fabG1*, *ahpC*, *gyrA*, *gyrB*, *rrs*, and *eis*) and another Xpert MTB/XDR assay. NGS will be performed from the culture isolate to obtain sequencing reads of high quality.

Figure 1. Phase II sample flow

≥ 3ml of sputum is required for the trial. This can be achieved through an individual sputum or pooling of serially collected sputa, homogenized with glass beads.

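### In Protocol Appendix 4, the 23% RIF-resistant share and the 21.5% and 1% KAN rates cannot all hold if RIF-resistant patients have one KAN rate across both stages

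*Protocol*

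**What the plan says.** Enrolment has two stages. Protocol section 6.1.2 says "Stage 1 will enrol 360 MTB-positive participants, irrespective of RIF resistance/sensitivity". Section 4 then adds "an additional subset of Xpert MTB-positive, RIF-resistant patients (n=400) will also be asked to participate in this study". The first stage therefore contains both RIF-sensitive and RIF-resistant patients, and the second only RIF-resistant ones.

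Appendix 4 turns this into expected counts for the 284 and 316 samples that remain after losses. Three of its inputs matter here:

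- RIF resistance in the first group: "Assume 23% of TB-positive samples are RIF-R based upon previous studies and data from these regions".
- KAN resistance in each group and in total, from the table row: "KAN-resistant 1% 3 21.5% 68 71".
- The footnote for the first group: "5% FQ resistance and 1-2% second-line injectable (AMK, KAN and CAP) resistance among TB-positive patients", which it converts to "3-6 second-line injectable-resistant specimens (limiting factor in sample size calculations").

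The totals, 71 KAN-resistant and 529 KAN-sensitive, become the KAN rows of Table 2 in Protocol section 9.1 and SAP section 10. Sensitivity there is 90% (80, 96) with width 16%, and specificity is 98% (96, 99).

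**The concern.** A group that is 23% RIF-resistant cannot have 1% KAN resistance overall if more than a fifth of its RIF-resistant members are KAN-resistant. The 1% and the 21.5% agree only if RIF-resistant patients in the first stage have a far lower KAN rate than those in the second, and no section states such a difference.

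KAN belongs to primary objective 1.3, and the KAN rows of Table 2 are the planned precision for it. Protocol section 9.3 and SAP section 6 also use the Table 2 intervals at interim: an estimate outside them leads to a data review by the Data Monitoring Committee. An inconsistent input therefore reaches a stated precision and a review trigger in two documents. The final intervals are not affected, because they will use the observed counts.

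**Working it through.** **Inputs (all from Appendix 4).** 284 and 316 included samples; RIF-resistant share of the first group 23%; KAN resistance 1% (first group) and 21.5% (additional group). The interval method, from the note to Table 2, is the 95% Wilson score with continuity correction.

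**Reproducing the plan.** 284 × 1% = 2.84, printed 3. 316 × 21.5% = 67.94, printed 68. 3 + 68 = 71, and 600 − 71 = 529. At 90% with n = 71 the interval is 80.0 to 95.5, width 15.5 points; the printed (80, 96) and 16% follow after rounding. The sums and the interval are right.

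**Consistency check.** For the first group, the KAN rate = 0.23 × (rate in RIF-resistant) + 0.77 × (rate in RIF-sensitive).

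- With 21.5% in RIF-resistant patients, the first term alone is 0.23 × 21.5% = 4.95%, and 4.945% × 284 = 14.0 samples.
- A total of 1% would need (1% − 4.945%) / 0.77 = −5.1% in RIF-sensitive patients, which is impossible.
- Rounding: the lowest product that the printed rates allow is 0.225 × 21.45% = 4.83%. The highest rate that prints as 1% is 1.5%.
- Without a shared rate, the first stage has 0.23 × 284 = 65.3 RIF-resistant samples, and 1% overall allows at most 1% / 23% = 4.3% of them to be KAN-resistant. That is 21.5 / 4.35 = 4.9 times lower than in the second stage (3.2 to 3.9 times at the rounding limits shown below).

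**The same check on every row.**

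| Row | Implied minimum in first group | Printed | Result |
|---|---|---|---|
| INH | 0.23 × 99% = 22.8% | 29% | fits |
| AMK/CAP | 0.23 × 9% = 2.07% (5.9) | 2% (6) | fits after rounding |
| FQ | 0.23 × 25% = 5.75% (16.3) | 5% (14) | marginally short |
| KAN | 0.23 × 21.5% = 4.95% (14.0) | 1% (3) | misses almost fivefold |

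For FQ the rounding limits nearly meet: 0.225 × 24.5% = 5.51% against 5.5%.

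**Consequence, by which input is wrong (sensitivity 90%).**

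- *The 1%.* The first group has at least 14 resistant and at most 270 sensitive. Totals: at least 14 + 68 = 82 resistant and at most 600 − 82 = 518 sensitive. Sensitivity interval 80.9 to 95.2, width 14.3 points. Specificity at n = 518 is 96.3 to 99.0, which still prints as (96, 99).
- *The 21.5%.* Nominally, 4.35% × 316 = 13.7, plus 2.84, gives about 17: interval 64.3 to 98.6, width 34.3 points. Rounding allows more. If the printed count of 3 means under 3.5, then 3.5 / 284 = 1.23%, 1.23% / 22.5% = 5.48%, and 5.48% × 316 + 3.5 = 20.8, about 21, width 30.5. If the printed 1% means up to 1.5%, then 1.5% / 22.5% = 6.67%, and 6.67% × 316 + 4.26 = 25.3, about 25, width 27.7.
- *The 23%.* The counts stay at 71 and 529. The RIF-resistant share is nominally at most 1% / 21.5% = 4.7%. Within rounding it is up to 1.23% / 21.45% = 5.7% or 1.5% / 21.45% = 7.0%.

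**The case against.** **The stages may differ.** The result depends on a shared KAN rate. Frozen samples are allowed if recruitment is slow (Protocol section 6.1.1), and the study may go on without a site that lags (section 10.4), so the mix could change between stages. That is possible, but Appendix 4 does not assume it. Both stages use the criteria of section 4.1, and section 5.3.1 describes the second as "followed by an additional, consecutive series of Xpert MTB/RIF RIF-resistant patients (n=316) between the three countries with participating clinical sites". The premise is reasonable but should be stated.

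**The table may not have been built on a shared rate.** Of the three second-line rows, AMK/CAP fits closely, FQ just misses and KAN fails. This weakens any claim about how the column was built. It does not make the KAN figures compatible under a shared rate.

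**A reader might infer that the 1% is the error and should be 5%.** The ordering points that way: KAN is below AMK/CAP in the first group (1% against 2%) but above it in the second (21.5% against 9%). Yet Protocol Table 1 defines KAN by *rrs* plus the *eis* promoter and AMK and CAP by *rrs* alone, and section 1.3 describes *eis* "promoter mutations exclusively associated with KAN resistance". This does not settle it. Under Protocol section 9.2.2 an isolate with phenotypic resistance and no recognised mutation still counts as resistant, so CAP resistance without KAN resistance can occur. The footnote also attributes the first-group rates to earlier studies and regional data. The 21.5% carries no source, but neither do the 99%, 25% and 9% beside it.

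**A reader might also infer that KAN precision is certain to be poor, or that 17 is a ceiling.** Neither holds. The wide interval arises only if the 21.5% is wrong, and 17 is a nominal figure that rounding raises to 21 to 25.

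**It changes little.** If the 1% is wrong, the width falls by about one point and nothing else in the plan moves. That stands, and it is why the point is minor.

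**Conclusion.** The point holds as an inconsistency among planning inputs, not as an error of addition. Given one KAN rate among RIF-resistant patients across both stages, 23% and 21.5% imply at least 4.95% (about 14 of 284) where the plan has 1% (3), and rounding cannot reconcile them. Which of the three inputs is wrong cannot be decided from the documents; the reversed order against AMK/CAP suggests the 1% without proving it.

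The severity is minor. If the 1% is wrong, the stated precision is slightly conservative and AMK/CAP (n = 34, width 23%) remains the limiting row. If the 21.5% is wrong, KAN becomes the limiting row and its printed width of 16% is too small by roughly 12 to 18 points. If the 23% is wrong, the KAN counts and precision do not change.

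**What to change.** 1. Check the 23%, 21.5% and 1% against the sponsor's sources, and cite a source for the 21.5%.
2. State in Appendix 4 whether RIF-resistant patients are assumed to have the same KAN rate in both stages and, if not, why.
3. Correct according to what the check shows:
   - *1% wrong:* first-group KAN at least about 5% (14 resistant, 270 sensitive); totals at least 82 and at most 518; Table 2 sensitivity 90% (81, 95), width 14%; specificity interval unchanged. Amend the footnote's 1-2% and 3-6 to match. The 760 stands.
   - *21.5% wrong:* replace the additional-group rate and count, and have Table 2 state the resulting precision (nominally about 17 resistant and a width of about 34 points; 21 to 25 and about 31 to 28 points within rounding).
   - *23% wrong:* keep 71 and 529 and correct the 23%.
4. Carry any changed KAN row into Table 2 of both the protocol and the SAP, since the interim review refers to its intervals.

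The cost is a source check, one sentence, one row and its footnote in Appendix 4, and at most the KAN rows of Table 2 in two documents. Enrolment does not change, and the FQ row needs no restatement on this ground.
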